12. EFFICACY ANALYSIS

12.1 Primary Objectives Analysis

The primary absolute efficacy objective will be evaluated using following null (H_0) and alternative (H_1) hypotheses:

$$H_0: 1 - HR = VE \leq 0.4 \quad \text{versus} \quad H_1: 1 - HR = VE > 0.4,$$

where HR is a hazard ratio of aQIV versus non-influenza comparator and VE is vaccine efficacy. The primary objective will be demonstrated if the lower limit of the two-sided confidence interval of VE estimate, with at least 95% coverage in a multiple sequential hypothesis testing, exceeds 40%. In case an interim analysis is performed, the 95% CI will be adjusted accordingly. If an interim analysis is performed and the trial doesn't stop, then all the subsequent analysis will be tested at a reduced alpha level, i.e. what's left from the interim analysis. The confidence interval will be higher than 95% instead of 95% for the final analysis.

Primary vaccine efficacy analyses will be based on the Efficacy FAS, and repeated on the Efficacy PPS.

The HR and the related 95% CI of HR, for onset of first RT-PCR confirmed influenza will be estimated by a proportional hazards regression model with treatment effect as a fixed effect and stratifying covariates as a random effect:

$h_i(t|X) = h_0(t) \exp(\beta^T X + b^T Z)$, with t denoting time to the influenza, β is the effect of treatment group indicated by X , b is random effect (assumed as a multivariable random gaussian variable with zero mean and diagonal covariance matrix), Z is random effect covariate (reflecting randomization strata, see [Section 8.1](#) for further discussion of the covariates utilised).

Subjects that did not experience ILI during observation period and subjects that dropped out from the study during observational period will be censored (right-censoring). The estimate of the hazard ratio, the respective estimate for absolute VE and the pertaining 2-sided CIs will be calculated based on this model. If the study continues over several seasons, estimates will be also adjusted for the factor season (s). In case of one or two (interim) analyses, confidence levels at each stage will be adjusted, as discussed in [section 14.1](#), to provide 95% overall coverage.

Estimates for hazard ratio in Cox Proportional hazard (PH) model will be calculated using Maximum Likelihood (ML) method. In case of problems with convergence (algorithm does not converge or converges to infinite estimates) penalized ML approach will be used ([Heinze and Schemper](#)).

$$\text{Vaccine efficacy } VE = 1 - HR, \text{ that is, } 1 - \exp(\widehat{\beta})$$

With $\hat{\beta}$ with $100(1 - \alpha)$ percent confidence interval as:

$[1 - \exp(+Z(\text{s.e.}(\hat{\beta}))); 1 - \exp(\hat{\beta} - Z(\text{s.e.}(\hat{\beta})))]$. Z is the $100(1 - \alpha)$ percent point of the standard normal distribution, and s.e. denotes the standard error of β

Primary analysis will take into account only first ILI episode for a subject. As exploratory evaluation, Cox PH model might be fitted taking into account recurrent ILI events.

In addition VE estimate estimated from Cox proportional model, a simple unadjusted estimate of VE will be also presented as $1 - \pi_{aQIV} / \pi_{Comp}$ along with 95% exact unconditional confidence interval; where π_{aQIV} and π_{Comp} will be attack rates for each group estimated as a binomial variable.

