5. SAMPLE SIZE AND POWER CONSIDERATIONS

Efficacy objectives:

Sample size and power consideration for the aQIV efficacy objective is based on criteria for demonstrating efficacy in placebo controlled studies provided in CBER guidance, specifically that the study should be powered to assess the lower bound of the two-sided 95% CI of vaccine effectiveness, anticipated to be substantially above zero. This study is planned using a group sequential design. The power of Cox Regression which is planned to be used for analysis is dependent on the overall number of influenza cases, so the sample sizes on number of subjects described in this section is provided more for operational reasons. Additional information on the planning of number of subjects that may need to be enrolled if it is decided to continue enrolment after interim analyses is described in [Section 8.6](#).

For the primary efficacy objective: with 1-sided alpha of 2.5% and assuming an attack rate of influenza of 3.5% among subjects enrolled in the non-influenza comparator group and 1.4% among the aQIV group, i.e. 60% assumed vaccine efficacy for aQIV, 238 events (i.e. 4,860 subjects per group under the assumed ERs) are needed with 86.5% power to show the absolute efficacy of aQIV versus non-influenza comparator, in preventing first occurrence RT-PCR-confirmed influenza A and/or B, due to any strain of influenza regardless of antigenic match to the strains in aQIV, in subjects ≥ 65 years of age, using a margin of 40% for lower bound of the CI for absolute vaccine efficacy.

For the first secondary efficacy objective: with a group vaccine efficacy of 65% but expecting conservatively reduced event rates of influenza cases due to matched strains of 2.5% among subjects in the non-influenza comparator group and 0.9% among the aQIV group then 144 events has estimated power approximately 88.5% to show the absolute efficacy of aQIV versus non-influenza comparator, using a margin of 40% for lower bound of the CI.

Assuming a drop-out rate of 10%, approximately 10,692 subjects ≥ 65 years, 5,346 per vaccine group will be randomized to receive either aQIV or non-influenza comparator (Boostrix®) in a 1:1 allocation ratio, stratifying by age (≥ 65 to 74 and ≥ 75 years of age), study site and by low vs high risk of influenza complications (score < 50 vs ≥ 50).

Immunogenicity objective:

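### SAP 12.1 uses the same alpha for the level of the two-sided VE interval and for its normal multiplier, so label and multiplier disagree for any alpha; taken literally at alpha = 0.05 it gives a 90% interval

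*SAP*

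**What the plan says.** SAP 12.1 (Primary Objectives Analysis) first sets the decision rule: "The primary objective will be demonstrated if the lower limit of the two-sided confidence interval of VE estimate" exceeds 40%. It requires a "two-sided confidence interval of VE estimate, with at least 95% coverage" under sequential testing, wider than 95% if an interim look was taken and the trial went on. The sentence introducing the Cox model speaks of "The HR and the related 95% CI of HR".

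Later in the same section the interval is written out. It is called a 100(1 − α) "percent confidence interval as" two limits, one using +Z × s.e. and the other −Z × s.e. Z is then defined as the 100(1 − α) "percent point of the standard normal distribution, and s.e. denotes the standard error of" the coefficient. α is given no number there. As extracted, the first limit also lacks the coefficient estimate.

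Elsewhere the level is one-sided. SAP 5 plans the primary test "with 1-sided alpha of 2.5% and assuming an attack rate of influenza of 3.5% among subjects enrolled in the non-influenza comparator group", and SAP 14.1 repeats one-sided 0.025. SAP 14.1, Table 1, gives example one-sided p-value boundaries of 0.00625 at 119 events and 0.02275 at 238. SAP 14.1 also says that PROC SEQTEST compares the test statistic with its boundaries and can supply confidence limits after the trial stops.

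**The concern.** A symmetric two-sided interval with coverage 1 − α leaves α/2 in each tail, so its multiplier is the 100(1 − α/2) percent point. The SAP puts the 100(1 − α) point on both sides, which leaves α in each tail and gives coverage 1 − 2α. The label and the multiplier cannot both be right.

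This is the only explicit formula in either document for the interval whose lower limit is compared with 40%. SAP 12.2 applies the same kind of lower-limit rule to the secondary objectives using a similar Cox model, so the key secondary objective inherits the ambiguity. A programmer asked for a 95% interval from a 100(1 − α) percent formula would naturally set α = 0.05, and the printed definition then returns 1.645. An interval built that way could clear 40% on data that fail the one-sided 2.5% test.

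**Working it through.** **Inputs.** Margin VE = 40%, i.e. HR 0.6: "using a margin of 40% for lower bound of the CI for absolute vaccine efficacy" (SAP 5). Design effect and information: "60% assumed vaccine efficacy for aQIV, 238 events" (SAP 5), i.e. HR 0.4. One-sided α 0.025 (SAP 5, SAP 14.1). Boundaries 0.00625 and 0.02275 for efficacy and 0.35022 for futility (SAP 14.1, Table 1). Stated power 86.5% (SAP 5).

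**1. Reproduce the plan's power, to see which multiplier it was planned on.** With 1:1 allocation, s.e.(log HR) ≈ 2/√238 = 0.1296, and the distance from margin to design effect is ln(0.6/0.4) = 0.4055, or 0.4055/0.1296 = 3.128 standard errors.
- Fixed design, Z = 1.960: Φ(3.128 − 1.960) = 87.9%.
- Fixed design, Z = 2.000 (one-sided 0.02275): Φ(1.128) = 87.0%.
- Two looks at 119 and 238 events, Table 1 boundaries, binding futility: power 86.45%, overall one-sided error 0.0250. This reproduces the stated 86.5%.
- Fixed design, Z = 1.645: Φ(1.483) = 93.1%, which does not match.

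The plan was therefore powered on a multiplier of about 1.96 to 2.00.

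**2. Apply the printed definition, Z = Φ⁻¹(1 − α); coverage = 2Φ(Z) − 1; nominal one-sided error = 1 − Φ(Z).**

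| α put into the formula | Label | Z as printed | Actual coverage | Nominal one-sided error |
|---|---|---|---|---|
| 0.05 | 95% | 1.645 | 90% | 0.050 |
| 0.025 | 97.5% | 1.960 | 95% | 0.025 |
| 0.0455 (= 2 × 0.02275) | 95.45% | 1.690 | 90.9% | 0.0455 |

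The last row is the adjusted two-sided level for the final look under Table 1. The correct multiplier there is Φ⁻¹(1 − 0.02275) = 2.000, with final-look error 0.02275.

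**3. Smallest observed VE that passes at 238 cases.** Solve ln(HR) + Z × s.e. = ln(0.6).
- s.e. = 2/√238: VE = 1 − 0.6 × exp(−Z × 0.1296), which is 53.5% for Z = 1.960 and 51.5% for Z = 1.645.
- s.e. from the observed case split, √(1/a + 1/b) with a = 238 × HR/(1 + HR) and b = 238 − a: HR = 0.4562 (VE 54.4%) for Z = 1.960, and HR = 0.4777 (VE 52.2%) for Z = 1.645.

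Either way the bar drops by about 2 points.

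**4. Chance of success at a true VE of 50%, single look.** Using the case-split cut-offs from step 3 and s.e. evaluated at HR 0.5: 25.3% with Z = 1.960 and 37.0% with Z = 1.645.

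**5. With an interim look.** With 0.00625 at 119 events and Z = 1.645 at 238, overall one-sided error is 0.048 (binding futility) to 0.052 (non-binding). With Table 1's 0.02275 at the final look it is 0.0250 to 0.0259.

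The 2.5% and 5% figures are nominal normal-theory values. A simulation of the Wald interval at 238 cases and HR 0.6, conditioning on total cases, gave 2.3% and 4.3%.

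**The case against.** A reader might infer that the plan as it stands builds its 95% interval with 1.645 and so doubles the type I error of the primary test. The documents do not support that. The formula gives α no value, and where the efficacy and interim text gives a number it is one-sided 0.025. With that value the printed words yield Z = 1.96, true 95% coverage and no inflation.

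The intended level is also fixed by other text. SAP 12.1 itself demands at least 95% coverage, which a 1.645 interval would breach. Protocol 8.2.1.2 requires the lower limit of a two-sided 95% interval. Protocol 8.4.2.2.3 takes repeated and final intervals from the group-sequential method. SAP 14.1 makes the boundary comparison through SEQTEST. The stated power fits 1.96 to 2.00 and not 1.645. No sample size, power or boundary in the plan depends on the formula.

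Conversion damage is a further possibility: the first limit has lost the coefficient estimate in the extracted text, so a lost "/2" cannot be ruled out. Against that, the 100(1 − α) expression reads cleanly and identically in both places, so loss is possible but not shown.

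All of this stands as a limit on the consequence. It does not remove the inconsistency. The α = 0.025 reading implies a 97.5% label that the efficacy sections never use. SEQTEST does not settle the matter either, because SAP 12.1 still states success through the interval, and a 1.645 interval could pass where the boundary test fails.

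**Conclusion.** The interval definition in SAP 12.1 is wrong as written: for any α its label and multiplier contradict each other. The size of the consequence depends on how it is read.

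- **α = 0.05, applied literally, with this interval deciding success:** coverage 90%, nominal one-sided error 5% instead of 2.5% at VE = 40%, and a passing bar at 238 cases about 2 VE points lower.
- **Adjusted two-sided level 0.0455, applied literally:** final-look error 0.0455 against the Table 1 boundary of 0.02275.
- **α = 0.025:** correct multiplier, wrong label, no effect on error.

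The inflation is conditional, and the rest of the plan shows that it was not intended. The point assumes that the source SAP reads as extracted. It matters because the formula sits behind the primary claim and should not be left to the programmer's choice of α.

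**What to change.** Check the source SAP for a lost "/2" and for the missing coefficient estimate. If it reads as extracted, amend SAP 12.1 before unblinding:

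- Define Z as the 100(1 − α/2) percent point of the standard normal, with α the two-sided level for that analysis stage: Z = 1.96 if no interim look was taken, otherwise the group-sequential critical value for that stage (2.000 in the Table 1 example), consistent with SEQTEST.
- Print both limits in full: lower VE limit = 1 − exp(β̂ + Z × s.e.(β̂)); upper VE limit = 1 − exp(β̂ − Z × s.e.(β̂)).
- State that SAP 12.2 uses the same definition.

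The cost is a one-line correction to the SAP, with no effect on conduct, sample size or data collection.

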7.2 Efficacy Assessment

Confirmation of influenza infection by RT-PCR or culture from a nasopharyngeal swab sample is necessary for the efficacy assessment in the study. Nasopharyngeal swab retrieval will be initiated after primary protocol-defined ILI has been identified. Primary protocol-defined ILI can occur at any time during the study and will be evaluated in each subject from Visit 1 (Day 1) through Study Termination. ILI symptoms will be captured during study visits. The ILI onset day is defined as the first day that the subject meets the primary protocol-defined ILI. The end date is defined as the date the last symptom resolves. A new ILI episode will only be taken into account after resolution of the previous one, as judged by the investigator (suggested interval between two ILI episodes is 14 symptom-free days).

Subjects with primary protocol defined ILI will have a NP swab collected for evaluation of the presence of influenza virus. NP swabs should be targeted for collection within 3 days from the ILI onset to ensure optimal viral yield, however samples will be accepted if collected up to 6 days following the day of ILI onset. NP swabs will not be taken beyond a total of 7 days (6 days following onset of ILI) as the level of virus detectable beyond this period can be negligible, particularly for influenza A.

All NP swabs collected from subjects with ILI will be shipped under pre-specified conditions in viral transport media to a qualified lab and stored for analysis for influenza.

NP swabs will be analyzed by RT-PCR and placed into culture. The result of the RT-PCR assay will be the presence or absence of influenza virus. The viral culture will be used for the purpose of viral expansion to enable phenotypic characterization of the influenza virus (e.g. antigenic match). Testing will be conducted by a designated laboratory in a blinded manner towards the treatment arm. Please see the Protocol Ancillary Document for name(s) and details.

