8.1.1.2 Primary Efficacy Endpoint(s)

The primary efficacy endpoint is the time to first-occurrence of RT-PCR-confirmed influenza from 21 through 180 days after vaccination or end of the influenza season, whichever is longer.

The end of the influenza season will be defined as the end of June for Northern Hemisphere (NH) influenza season and end of December for Southern Hemisphere (SH) influenza season. For tropical countries, with no typical NH or SH influenza season, the season is defined by the use of the strains in the vaccine formulation (i.e. strains as recommended for the NH or the SH influenza season) and the timing of vaccination.

An influenza event is defined as RT-PCR- or culture-confirmed influenza infection in the setting of an influenza-like illness (ILI). The primary protocol-definition of ILI will be used to define success for the primary and key secondary efficacy endpoint.

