2.1.2 Primary Efficacy Endpoints

The primary efficacy endpoint is the time of first-occurrence of RT-PCR-confirmed influenza due to A (H1N1 and H3N2) or either B lineage due to any strain of influenza regardless of antigenic match to the strains selected for the seasonal vaccine from 21 through 180 days after vaccination or end of the influenza season, whichever is longer.

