- If the number of first-occurrence RT-PCR confirmed influenza cases from 21 through 180 days after vaccination or until the end of the influenza season, whichever is longer, is greater or equal to 120 but less than 238 unblinded interim analyses for efficacy and futility will be performed by the DMC (see below for description).

- If the number of first-occurrence RT-PCR confirmed influenza cases from 21 through 180 days after vaccination or until the end of the influenza season, whichever is longer, is greater or equal to 238 (targeted number of cases to be able to evaluate the primary objective) the trial will be stopped, data will be unblinded and the final analysis will be performed by the Sponsor. If the trial proceeds to the final analysis (upon reaching 238 cases) the boundaries for acceptance or rejection are identical to the assumed type 1 and type 2 errors for the overall design, and the trial stops to either reject or not reject the null hypothesis of the primary objective. That is, the primary objective, i.e. VE against RT-PCR confirmed influenza A and or B will be assess the one-sided 0.025 alpha level.

If the DMC states that the observed data provides already the full information level needed for the final test decision, then the final analysis can be done on full alpha level of one-sided 0.025 and no further enrollment is needed. However if the decision of the group-sequential test is to continue the study then it is on the DMC to determine the number of subjects needed to be additionally enrolled. The DMC should not be influenced by the results of the efficacy testing at the interim analysis when planning further subjects' accrual or the times of future analysis. Only the overall number of cases is allowed to be used for further planning. The following formula for determination of sample sizes for further enrollment may be used:

$$N_{\text{total}} = (C_{\text{planned}} - C_{\text{observed}}) / ER,$$

where N_{total} denotes the total number of subjects needed for further enrollment, C_{planned} is the overall number of cases needed for the test, i.e. 238 cases, C_{observed} is the number of cases observed at current stage, and ER is the observed total attack rate for both groups combined. A drop-out rate of 10% should be added.

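### Read literally, SAP 12.1 limits the primary analysis to each subject's first ILI episode, which conflicts with an endpoint, model and case trigger based on first RT-PCR-confirmed influenza

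*SAP*

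**What the plan says.** SAP 2.1.2 sets the endpoint: "The primary efficacy endpoint is the time of first-occurrence of RT-PCR-confirmed influenza". Protocol 8.1.1.2 agrees: "The primary efficacy endpoint is the time to first-occurrence of RT-PCR-confirmed influenza from 21 through 180 days after vaccination", or to the end of the season if that is later. SAP 12.1 opens its model description in the same terms; the hazard ratio "for onset of first RT-PCR confirmed influenza will be estimated by a proportional hazards regression model". SAP 14.1 triggers the interim and final analyses on the "number of first-occurrence RT-PCR confirmed influenza cases from 21 through 180 days after vaccination or until the end of the influenza season".

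Later in SAP 12.1, after the confidence interval formula, comes the sentence at issue: "Primary analysis will take into account only first ILI episode for a subject". It mentions neither RT-PCR nor the window. The sentence after it offers a Cox model for recurrent ILI events as a possible exploratory analysis. The censoring rule in SAP 12.1 is also written in terms of ILI: "Subjects that did not experience ILI during observation period and subjects that dropped out from the study during observational period will be censored".

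Repeat episodes are expected. Protocol 7.2 says: "A new ILI episode will only be taken into account after resolution of the previous one". Protocol 5.2.1 provides a new booklet at the ILI visit in case of another ILI, and Protocol 3.5 has swabs taken from Day 1.

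**The concern.** ILI and RT-PCR-confirmed influenza are different things in this trial. An ILI needs only one respiratory and one systemic symptom, for example cough with tiredness, and many causes other than influenza can produce that. Surveillance is weekly through Day 181 or the end of the season. Some subjects can therefore have an RT-PCR-negative ILI first and confirmed influenza later.

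For such a subject the plan gives two answers. Under the endpoint, the model description and the trigger count, the later illness is a primary case. Under the first-episode sentence it is not. The censoring rule does not settle the matter, because it names only subjects without ILI and dropouts; a subject with an RT-PCR-negative ILI is in neither group.

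Two programmers could thus build different event datasets for the one analysis that decides success. The trial could stop at 238 cases while its deciding model holds fewer, and a choice made after unblinding would be post hoc.

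**Working it through.** **Inputs (SAP 5 and SAP 14.1, Table 1).** Attack rates 3.5% and 1.4% (VE 60%, HR 0.4); margin VE 40% (HR 0.6); one-sided alpha 0.025; 4,860 per group; 238 events; stated power 86.5%; boundaries 0.00625 (efficacy) and 0.35022 (futility) at 119 events and 0.02275 at 238.

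**Reproducing the plan.**
- Events: 4,860 × (0.035 + 0.014) = 238.1.
- Fixed-sample power with the equal-split approximation: Φ(ln(0.6/0.4) × √238 / 2 − 1.96) = Φ(3.128 − 1.96) = 87.9%. At 0.02275 it is 87.0%.
- Two-stage calculation with the SAP boundaries: power 86.45%, type I error 0.0250.

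The stated 86.5% is reproduced. It rests on all first RT-PCR-confirmed cases, with no deduction for cases that follow an earlier ILI.

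**Loss under the literal sentence.** The documents give no non-influenza ILI rate, so the following is assumed: a cumulative incidence q by Day 180, constant hazard λ = −ln(1 − q)/180 from Day 1, the same in both arms and independent of influenza; influenza onset spread evenly over Days 21 to 180. The share of cases with an earlier ILI is the mean over t from 21 to 180 of 1 − exp(−λt). Power is Φ(ln(1.5) × √D / 2 − 1.96), where D is the number of events left.

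| q | Cases lost | Events left of 238 | Power |
|---|---|---|---|
| 0 | 0 | 238 | 87.9% |
| 10% | 5.7% | about 224 | 85.9% |
| 20% | 11.6% | about 210 | 83.7% |
| 30% | 17.7% | about 196 | 81.0% |

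**The part before Day 21.** The table counts ILI from Day 1. SAP 12.1 does not define the start of its observation period. If it starts at Day 21, an ILI before then plays no part, and the share lost is 1 − (1 − exp(−159λ))/(159λ), where 159 = 180 − 21:

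| q | Cases lost | Events left | Power |
|---|---|---|---|
| 10% | 4.5% | about 227 | 86.4% |
| 20% | 9.2% | about 216 | 84.6% |
| 30% | 14.2% | about 204 | 82.6% |

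Most of the loss therefore comes from RT-PCR-negative ILI inside the window and does not depend on that definition.

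**Bias.** With equal non-influenza ILI rates, simulated VE under the literal rule stays at about 60%. With 10% more of it in the aQIV arm (22% against 20%, or 33% against 30%), estimated VE rises by under 1 percentage point.

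**The case against.** The strongest reply is that the sentence is loose wording and not a rule. SAP 12.1 has already named the event as the first RT-PCR-confirmed influenza, and the endpoint and the triggers agree. Read with the exploratory sentence that follows, it may only separate a first-event analysis from a recurrent-event one.

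The documents also use ILI as shorthand for confirmed cases. The protocol synopsis states the primary hazard ratio in terms of protocol-defined ILI. Protocol 8.6 speaks of planned ILI cases where SAP 14.1 has RT-PCR-confirmed influenza cases, and both describe the 119 interim events as confirmed ILIs. A literal reading would make the exploratory model an all-cause ILI analysis, although Protocol 8.4.4.2 lists no exploratory efficacy objectives. The protocol itself contains no first-episode restriction.

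Much of this stands. It makes the first confirmed episode the probable intent, and it makes the loss conditional on a literal reading. It does not remove the conflict. Elsewhere the SAP adds the qualifier when it means confirmed illness (2.1.3, 13 and 13.3); here it does not, and nothing defines the first ILI episode as the first confirmed one.

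A reader might infer that the plan definitely discards endpoint cases. The documents do not support that, because it requires one sentence to override the endpoint and the model description. Nor do they show that earlier non-influenza ILI will be common, since they give no rate.

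**Conclusion.** The sentence is wrong as written. Applied literally, it excludes from the deciding model any RT-PCR-confirmed case that follows an RT-PCR-negative ILI in the window, although that case meets the endpoint and counts toward 238.

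Under the assumptions above, counting ILI from Day 1, a non-influenza ILI incidence of 10% to 30% costs about 14 to 42 of the 238 events and about 2 to 7 points of power from 87.9%. The cost is somewhat smaller if observation starts with the window. These sizes are illustrations, because the ILI rate is assumed.

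A reader might also infer a biased efficacy estimate. The check does not support this: with equal ILI rates in the two arms the estimate is essentially unchanged, and the cost is events and precision.

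The case for correction rests on the ambiguity in the primary event rule and not on the size of the loss, which alone would not make this a critical defect.

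**What to change.** Replace the sentence in SAP 12.1 with: *The primary analysis will take into account only the first RT-PCR-confirmed influenza episode per subject with protocol-defined ILI onset in the primary window; an earlier ILI that was RT-PCR negative or not tested neither counts as an event nor ends follow-up.*

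Then:
- Align the censoring rule in SAP 12.1, so that subjects without RT-PCR-confirmed influenza in the window are censored, and say when the observation period starts.
- State separately, before unblinding, how RT-PCR-confirmed influenza with onset before the window is handled. The replacement sentence leaves this open on purpose; otherwise a second infection could enter as a first occurrence without anyone having decided so.
- Change the exploratory sentence from recurrent ILI to recurrent RT-PCR-confirmed influenza.
- Use parallel wording, with culture confirmation and antigenic match, for the key secondary endpoint.

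The cost is a few sentences of SAP text. No new data are needed, because the protocol already has later episodes swabbed and tested.
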